#### CONFIDENTIAL

Version Date: September 27, 2019

wake times are often determined by external demands, such as work schedules.

• Arrange for the weekly phone or WebEX videoconferencing meeting to administer the intervention for the following week.

#### 7.3.3.4 Week 4

- Participant will initiate new sleep schedule as prescribed by the study team.
- See Table 6 for study related procedures.
- Send daily text message or email reminders via a secure email server to participants to complete their daily sleep diary as needed.
- Record participant's adherence to the intervention program.
- Record adverse events as reported by participant or observed by investigator.
- Arrange for the weekly phone or WebEx videoconferencing meeting to administer the intervention for the following week.

Table 6: SASI Data Collection Weeks 4 – 13			
	Number of times to complete per week	Number of questions	Estimated time
Fitbit	Wear 24/7	n/a	n/a
Daily sleep diary	7	9	< 5 minutes/day < 35 minutes/week
PROMIS Fatigue 6a morning	1	6	< 5 minutes/week
PROMIS Fatigue 6a evening	1	6	< 5 minutes/week
Epworth Sleepiness Scale	1	8	< 5 minutes/week
TOTAL TIME			< 50 minutes/week

#### 7.3.3.5 Weeks 5-13

- Participant will initiate new sleep schedule each week as prescribed by study team.
- See Table 6 for study related procedures.
- Send daily text message or email reminders via a secure email server to participants to complete their daily sleep diary as needed.
- · Record participant's adherence to the intervention program.
- Record adverse events as reported by participant or observed by investigator.
- Arrange for the weekly phone or WebEx videoconferencing meeting to administer the intervention for the following week
- Week 13: Arrange for the delivery of the accelerometry devise by the study team or UPS.

#### 7.3.3.6 Week 14

- Participant will initiate new sleep schedule as prescribed by the study team.
- See Table 7 for study related procedures.
- Send daily text message or email reminders via a secure email server to participants to complete their daily sleep diary as needed.
- Arrange for the weekly phone or WebEX videoconferencing meeting to administer the intervention for the following week.
- Record participant's adherence to the intervention program.
- Record adverse events as reported by participant or observed by investigator.

Table 7: Data Collection Week 14			
	Number of times to complete per week	Number of questions	Estimated time
Wrist accelerometer and fitbit	Wear 24/7	n/a	n/a
Daily sleep diary	7	9	< 5 minutes/day < 35 minutes/week

Version Date: September 27, 2019

TOTAL TIME			< 50 minutes/week
Epworth Sleepiness Scale	1	8	< 5 minutes/week
PROMIS Fatigue 6a evening	1	6	< 5 minutes
PROMIS Fatigue 6a morning	1	6	< 5 minutes

#### 7.3.3.7 Week 15

- Participant will initiate new sleep schedule as prescribed by the study team.
- See Table 8 for study related procedures
- Send daily text message or email reminders via a secure email server to participants at a mutually agreed upon time to remind them to complete their daily sleep diary.
- · Record participant's adherence to the intervention program.
- Record adverse events as reported by participant or observed by investigator.
- Arrange for the return of the accelerometry devise to the study team or UPS
- Arrange for a date and time for the final CTSI visit 2 (Time Point 2, post-intervention) within three weeks of completing the intervention

Table 8: Data Collection Week 15			
	Number of times to complete per week	Number of questions	Estimated time
Wrist accelerometer and fitbit	Wear 24/7	n/a	n/a
Daily sleep diary	7	9	< 5 minutes/day < 35 minutes/week
PROMIS Fatigue 6a morning	1	6	< 5 minutes
PROMIS Fatigue 6a evening	1	6	< 5 minutes
Epworth Sleepiness Scale	1	8	< 5 minutes
36-item Short Form Health Survey (SF-36) version 1	1	36	40 minutes
ASA24	1	varies	24 minutes
Demographics – SDOH: Alcohol use (AUDIT C)	1	3	< 5 minutes
Demographics – SDOH: Tobacco use	1	2	< 5 minutes
Index of Self-Regulation	1	9	5 minutes
SAFTEE	1	128	10 minutes
PROMIS Depression 6a	1	6	< 5 minutes
TOTAL TIME ~140 minutes/week			~140 minutes/week

#### 7.4 Final Study Visit (within 3 weeks of completing SASI): Duration < 60minutes

- Record any new medications prescribed during the study period to treat hyperglycemia, hypertension, hypertriglyceridemia, or low HDL-c.
- See Table 10 for study related procedures.
- Record adverse events as reported by participant or observed by investigator.
- Notify participant that aggregate-level results will be available after dissemination of study findings begins.
- Instruct participant to report any subsequent event(s) that the participant, or the participant's
  physician, believes might reasonably be related to participation in this study.

Table 10: Final Study Visit (at home)		
	Number of questions	Estimated time
Acceptability survey (post intervention)	7	< 5 minutes

Version Date: September 27, 2019

Open ended interview	varies	30 minutes
TOTAL TIME		~ 35 minutes

#### 7.5 Withdrawal Visit

If a participant withdraws or is withdrawn from the study, no further study visits or procedures will be completed.

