#### 1.3 Potential Risks & Benefits

#### 1.3.1 Known Potential Risks

This study involves no more than minimal risk, as defined by federal regulations, to research participants. The probability and magnitude of harm or discomfort anticipated for this research are not greater than what the population encounters in daily life or during the performance of physical or psychological examinations or tests. The only alternative to study participation is non-participation. Non-participation will in no way affect the potential participant's medical care.

Loss of confidentiality. To protect against loss of confidentiality all survey data and clinical assessment data will be entered directly into REDCap (Research Electronic Data Capture). REDCap is a secure, web-based application designed to support data capture and storage for research studies, providing 1) an intuitive interface for validated data entry; 2) audit trails for tracking data manipulation and export procedures; 3) automated export procedures for seamless data downloads to common statistical packages; and 4) procedures for importing data from external sources. REDCap has been designed to allow for compliance with such standards as HIPAA, 21 CFR Part 11, and international standards. Also included are a built-in project calendar, a scheduling module, ad hoc reporting tools, and advanced features, such as branching logic, file uploading, and calculated fields. For further information about protecting against the risk of loss of confidentiality, please see Section 8.8

Protection Participant Confidentiality. Audiotaped intervention sessions that will be used to ensure the quality of the intervention and judge treatment fidelity will be reviewed by [name] and the PI and subsequently destroyed.

Discomfort. To protect against discomfort associated with the accelerometer, participants will be instructed in person during their CTSI intake visit on the use of these devices. Participants will be given verbal as well as written, illustrated instructions for using the devices. Study team 24/7 contact information will also be provided to assist with troubleshooting. Participants may also remove the accelerometer and note this in their sleep diary.

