## 3 Study Design and Endpoints

#### 3.1 Description of Study Design

This single site, one group, pilot study will test the acceptability and feasibility of the Self- management for Adequate Sleep Intervention (SASI) in racially/ethnically diverse middle-aged adults with MetS.

This is an 18-week study. In the first 2 weeks, baseline data will be collected. During week 3, the baseline data will be used to confirm study eligibility based on objectively estimated short sleep and to plan the personalized intervention. During weeks 4 to 15, the study team will call or videoconference participants once a week to prescribe a sleep schedule based on their daily sleep diaries. At the end of week 15, participants will be asked to schedule their final visit within 3 weeks.

Version Date: September 27, 2019

Acceptability data will be collected at two time points (i.e., pre- intervention and at the final visit). The final visit will include a 30-minute open ended interview to explore perceived facilitators and barriers to implementing SASI. The intake visit will take place at the CTSI. The final visit will take place using video conferencing technology such as WebEx. Weekly contact with the study team will take place during the intervention weeks so that SASI can be personalized based on individual responses to the sleep intervention. This weekly contact will be remote in the form of telephone calls or remote video conferencing technology.

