#### 3.2.3 Exploratory Endpoints

Exploratory endpoints are the perceived barriers and facilitators of SASI. These will be identified through bivariate correlations between specific socio-ecological factors associated with sleep duration changes. Qualitative data analysis from the post intervention interviews will be conducted. Identifying perceived barriers and facilitators will lead to future tailoring and/or targeting of SASI.

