#### 4.5.2 Handling of Participant Withdrawals or Termination

Participants will be considered withdrawn if they cannot be contacted for 4 weeks during the intervention using all of the contact information collected. No further efforts will be made to contact the participant and that participant will be considered lost to follow-up. Abrupt termination of participation in the study intervention poses no safety risk to participants. As this study is minimal risk, efforts will not be made to collect safety and efficacy data after withdrawal.

Any data collected before withdrawal from the study will be retained for analysis, and no new data will be collected. If the participant requests that data be destroyed, all paper records will be shredded, and any data already processed into computer files will be removed. However, if results based on the participant's data have been submitted for publication or presentation before the request is made, the results cannot be removed from the publication or presentation.

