#### 5.1.2 Procedures for Training Interventionalists and Monitoring Intervention Fidelity

The PI and trained study team members will be responsible for administering the intervention. We will use recommendations of the Treatment Fidelity Workgroup of the NIH Behavior Change Consortium^45 to enhance SASI fidelity. The treatment fidelity plan includes audiotaping of each SASI session and reviewing content against an a priori performance checklist to ensure consistency in SASI delivery. Treatment fidelity will be monitored by the research team with guidance from [name], Co-investigator. Barriers to implementing SASI will be identified and resolved together with the participant and the PI or Co-I's.

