## 12.2 Statistical Hypotheses

The sample size is too small to make inferences about relationships evaluated in the pilot study to the larger population of middle aged adults with MetS. For the primary aim, acceptability will be evaluated by the percentage of participants rating SASI as acceptable (overall acceptability survey scores greater than 21), neutral (overall acceptability survey scores equal to 21), and unacceptable (overall acceptability survey scores less than 21) on the Acceptability Survey at each of two time points (pre-intervention and post intervention). Feasibility will be evaluated by the 1) recruitment rate: the percentage of potential participants screened in order to enroll 60 participants with evaluable data, 2) attrition rate: the percentage of enrolled participants completing the 18-week study. Participants will be considered withdrawn after 4 weeks of not responding to phone calls/emails during the intervention, and the 3) protocol adherence rates; the percentage of participants completing greater than or equal to 4 daily sleep diary entries per week for 80% or more of the intervention period. For the secondary endpoints, paired t-tests will be used to compare the mean preintervention and mean post-intervention estimates for SAFTEE scores, physical activity, sedentary behavior, diet quality, smoking, alcohol use, affective well-being, morning fatique, evening fatique, and self- regulation measurements. For the exploratory endpoints of perceived barriers and facilitators of SASI, bivariate correlations between specific socio-ecological factors and sleep duration change will be identified. The qualitative data from the post intervention interviews will be analyzed using content analysis. Content analysis includes a line- by-line review that yields clusters of data that are coded. This coding is linked to interview questions. Summarization of coding will be performed across individual interviews, and subsequently crossclassified to yield a rich descriptive analysis. Emerging themes within and across interviews will be identified, and review of fit with data verified.

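### Perceived barriers to SASI are elicited for analysis only from participants who reach the final-visit interview, and the barriers raised at weekly calls are not named as data

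*Combined protocol and SAP*

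**What the plan says.** **The barrier endpoint.** Section 3.2.3 makes perceived barriers and facilitators the exploratory endpoint, with later tailoring of SASI as the purpose. It names two analyses. One correlates socio-ecological factors with change in sleep duration. The other is qualitative: "Qualitative data analysis from the post intervention interviews will be conducted". Section 12.2 gives the method: "The qualitative data from the post intervention interviews will be analyzed using content analysis".

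**When the interview happens.** Section 3.1: "The final visit will include a 30-minute open ended interview to explore perceived facilitators and barriers to implementing SASI". Section 7.4 (Table 10) places it in the final visit, within three weeks of completing SASI.

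**What happens on withdrawal.** Section 7.5: "If a participant withdraws or is withdrawn from the study, no further study visits or procedures will be completed". Section 4.5.2: "Any data collected before withdrawal from the study will be retained for analysis, and no new data will be collected". For people who cannot be reached for four weeks during the intervention, the same section adds: "No further efforts will be made to contact the participant".

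**What the weekly sessions cover.** Under Section 5.1.1, each session includes discussion of difficulties in carrying out the intervention. Section 5.1.2 adds: "Barriers to implementing SASI will be identified and resolved together with the participant and the PI or Co-I's". Neither Section 3.2.3 nor Section 12.2 uses this material. Section 1.3.1 refers to "Audiotaped intervention sessions that will be used to ensure the quality of the intervention and judge treatment fidelity" and says they are destroyed after review. Section 6.1.1 says that 20% of sessions will be reviewed, for fidelity.

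**Attrition.** Section 12.4.2 treats attrition above 20% as suggesting lack of feasibility and plans to look at attrition in subgroups that it does not name.

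**The concern.** Attrition is one of the feasibility measures, and the barrier findings are meant to shape the next version of SASI. A participant who stops because the schedule could not be made to work is a natural person to ask about barriers. Under the plan that participant is not interviewed and is not asked why they left, and what they told the facilitator beforehand does not enter the content analysis. Section 10.8 records a reason for exclusion for people screened, but no section asks for a reason for withdrawal.

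If attrition passes the 20% limit, the study would know how many people left and some of their characteristics, but would hold for analysis no participant's account of why. The barrier list passed to the later trial would describe those who stayed. The information also cannot be recovered afterwards, so it has to be captured during conduct.

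**Working it through.** **1. Who can supply each barrier source**

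| Source | Where defined | What it needs | Leaves before week 14 | Leaves after week 15, before the final visit |
|---|---|---|---|---|
| Interview | 3.1, 7.4, 12.2 | Attendance at the final visit | No | No |
| Correlation with sleep change | 3.2.3, 12.2 | A pre and a post sleep value | No, if the 12.4.3 window applies | Yes |
| Weekly session discussion | 5.1.1, 5.1.2 | Attendance at calls | Yes, up to the last call | Yes |

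The third row is the only one that covers every participant who has had a call, and it is the one not named as data. The second row rests on an inference: Sections 3.2.3 and 12.2 set no window for sleep change. The last-two-weeks window is in Section 12.4.3, where it defines the secondary endpoint.

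**2. The plan's own sample figure**

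Inputs (Section 4): 220 recruited, 65% ineligible, 20% lost during the intervention, 60 evaluable.

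- Starters: 220 × (1 − 0.65) = 77
- Evaluable: 77 × (1 − 0.20) = 61.6, close to the stated 60
- Lost: 77 × 0.20 = 15.4
- Reverse check: 60 / 0.80 = 75 starters, so 15 lost; 75 / 0.35 = 214 screened, close to 220

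Both routes give about 15 people, or 20% of starters, without an interview. The expected rate sits exactly at the feasibility limit in Section 12.4.2. If attrition were 10% or 30% instead (my assumption), the number would be 77 × 0.10 = 7.7 or 77 × 0.30 = 23.1, so roughly 8 to 23.

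**3. Effect on the picture of barriers (illustration with assumed rates)**

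Suppose a barrier affects 60% of dropouts and 20% of completers. Prevalence among starters is 0.20 × 0.60 + 0.80 × 0.20 = 0.28, but completer interviews would show 0.20. With 50% and 30%, the figures are 0.20 × 0.50 + 0.80 × 0.30 = 0.34 against 0.30. The documents give no rates, so these show direction and rough size only.

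**4. Chance of hearing a barrier at all from dropouts (assumed rates)**

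The chance that a barrier with prevalence p appears at least once among n dropouts who answer is 1 − (1 − p)^n.

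- n = 15: p = 0.20 gives 0.96; p = 0.10 gives 0.79
- n = 8: p = 0.20 gives 0.83; p = 0.10 gives 0.57

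Fifteen is a ceiling, since some will decline or be unreachable. Under the present plan n = 0.

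**The case against.** The strongest reply is that dropouts are far from absent from the data, and most of that reply stands.

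- **Retained data.** Section 4.5.2 keeps everything collected before withdrawal. The economic, family, sleep-environment and morningness surveys are completed in baseline weeks 1 or 2 (Section 7.3.3, Table 4). Diaries and weekly fatigue and sleepiness scores run until the person leaves, and attendance is tracked (Section 5.1.3). With the subgroup look at attrition in Section 12.4.2, correlates of dropout can be examined. A reader might infer that the barriers behind dropout cannot be found, or that withdrawals contribute nothing to this objective. The documents do not support either reading. What is missing is the participant's own account, which is what a perceived barrier is, and comparisons resting on about 15 dropouts would be imprecise.
- **Recordings.** A reader might infer that destroying recordings singles out withdrawals. It does not: it applies to everyone's reviewed recordings and is listed as a confidentiality protection. Nothing forbids session notes.
- **Who is interviewed.** It would also go too far to say that only people who coped are interviewed. Withdrawal for non-response takes four weeks of silence, so someone who adhered poorly can still reach the final visit.
- **Why people leave.** Section 4.5.1 allows termination for adverse events, other medical conditions or a newly met exclusion criterion. Those cases need not reflect barriers to SASI, so 15 is an upper bound.
- **Open specification.** Section 12.1 calls Section 12 an overview with a formal SAP to follow, so coding of session content is unspecified rather than excluded. Sections 12.3 and 12.4.1 include all participants and allow imputation, but neither can supply an interview that was not held.
- **Limits of an exit interview.** Section 1.3.1 promises that people may leave without giving a reason, and those who go silent would not be reached.

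The objective is exploratory, and no primary or secondary endpoint changes.

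**Conclusion.** The point holds in a limited form. Followed as written, the plan yields an account of perceived barriers from final-visit attenders only. It collects no reasons for withdrawal and leaves the weekly discussion of difficulties outside the analysis. Up to about 15 of 77 starters (20%) are affected, assuming the plan's 65% and 20% rates; 10% to 30% attrition would give about 8 to 23. How many of these leave because of a barrier is unknown. That the correlation analysis also loses early leavers is likely, but depends on the Section 12.4.3 window being the one used.

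This is an inexpensive improvement to an exploratory objective and no threat to the study's main conclusions. It is worth making because the information exists only while calls are taking place.

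**What to change.** **Main change**

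1. In Sections 7.3.3.4 to 7.3.3.7, have the facilitator enter the difficulty or barrier raised at each weekly call, or that none was raised, in a REDCap field. Adherence is already recorded in each of these weeks.
2. In Sections 3.2.3 and 12.2, name this log as a source for the content analysis for all participants, including those who later withdraw.
3. Report barriers separately for completers and withdrawals, and keep log entries distinguishable from interview material.

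**Optional addition.** In Sections 7.5 and 4.5.2, allow one freely refusable question on the reason for leaving, asked only at voluntary withdrawal and worded to respect the promise that no reason need be given. Both sections need matching wording, since both now rule out anything new after withdrawal.

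**Cost.** A short amendment, a consent line if the IRB asks for one, one field per existing call, and some added coding. No extra visit or staff is needed, and recordings can still be destroyed as planned. The limits are that log entries are the facilitator's summary and not the participant's words, and that nothing is learned after the last call from those who go silent.

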#### 7.6 Unscheduled Visit

Not applicable.

#### 7.7 Concomitant Medications, Treatments, and Procedures

Any medications prescribed by treating health care provider for hyperglycemia, hypertension, hypertriglyceridemia, or low HDL-c levels during study participation will be recorded on the case report forms (CRFs). For this protocol, a prescription medication is defined as a medication that can be prescribed only by a properly authorized/licensed clinician.

## 8 Assessment of Safety

#### 8.1 Specification of Safety Parameters

The study will involve no more than minimal risk to research participants. The probability and magnitude of harm or discomfort anticipated for this research are not greater than what this same population encounters in daily life or during the performance of physical or psychological examinations or tests. The only alternative to study participation is non-participation.

#### 8.1.1 Definition of Adverse Events (AE)

An **adverse event** (AE) is any symptom, sign, illness or experience that develops or worsens in severity during the course of the study. Intercurrent illnesses or injuries should be regarded as adverse events. Abnormal results of diagnostic procedures are considered to be adverse events if the abnormality:

- · results in study withdrawal
- is associated with a serious adverse event
- · is associated with clinical signs or symptoms
- · leads to additional treatment or to further diagnostic tests
- · is considered by the investigator to be of clinical significance

